### 10.2 SECONDARY EFFECTIVENESS VARIABLES

There will be no imputation of missing data before analyses on the following variables. Subjects with missing data for a given variable will be excluded from analysis on that variable.

#### 10.2.1 VALIDATION OF RATER'S ASSESSMENT

To assess the rater's assessment of improvement, a total of five clinicians will review the 2D photography at both baseline and Day 60. Two of the five will be unblinded and will have knowledge of which photos are from which visit. The other three will remain blinded to the visit. All raters will be compared using Cohen's unweighted kappa statistic. Based on the Landis et al. scale, a substantial or almost perfect agreement among raters will validate the method.

#### 10.2.2 PHYSICIAN – GLOBAL AESTHETIC IMPROVEMENT SCALE SCORES (P-GAIS)

Physician will report P-GAIS on a scale of 1-5 at Days 60, 90 and 180. Tables will summarize this in both the ITT and PP populations at each visit. The summary will include the number and percentage of subjects in each of the 5 categories and the two-sided Clopper-Pearson 95% CI of the percentages. A binomial test of proportions will be carried out for those scoring 3 or greater verse those scoring 2 and lower.

### *10.2.3 SUBJECT – GLOBAL AESTHETIC IMPROVEMENT SCALE SCORES (S-GAIS)*

As in section 10.2.2, subjects will report S-GAIS on a scale of 1-5 at Days 60, 90 and 180. Tables will summarize this in both the ITT and PP populations at each visit. The summary will include the number and percentage of subjects in each of the categories and the two-sided Clopper-Pearson 95% CI of the percentages. A binomial test of proportions will be carried out to compare those assessed with improvement versus no improvement. Additionally, a binomial test of proportions will test satisfaction, by testing those grouped as “Satisfied” or “Very Satisfied” verse all others. Further, likelihood of recommendation will be tested amongst those responding “Likely” or “Very Likely” verse all others.

### *10.2.4 PHYSICIAN – GLOBAL SATISFACTION QUESTIONNAIRE (P-GSQ)*

Physician will fill out the P-GSQ at Days 60, 90 and 180. Tables will summarize this in both the ITT and PP populations at each visit. The summary will include the number and percentage of subjects in each of the categories and the two-sided Clopper-Pearson 95% CI of the percentages. A binomial test of proportions will be carried out to compare those assessed with improvement versus no improvement. Additionally, a binomial test of proportions will test satisfaction, by testing those grouped as “Satisfied” or “Very Satisfied” verse all others. Further, likelihood of recommendation will be tested amongst those responding “Likely” or “Very Likely” verse all others.

### *10.2.5 SUBJECT – GLOBAL SATISFACTION QUESTIONNAIRE (S-GSQ)*

Subjects will fill out the S-GSQ at Days 60, 90 and 180. Tables will summarize this in both the ITT and PP populations at each visit. The summary will include the number and percentage of subjects in each of the categories and the two-sided Clopper-Pearson 95% CI of the percentages. A binomial test of proportions will be carried out to compare those assessed with improvement versus no improvement. Additionally, a binomial test of proportions will test satisfaction, by testing those grouped as “Satisfied” or “Very Satisfied” verse all others. Further, likelihood of recommendation will be tested amongst those responding “Likely” or “Very Likely” verse all others.

### *10.2.6 QUALITATIVE ASSESSMENT BASED ON 2D PHOTOGRAPHY*

Subjects will have 2D photographs taken at screening, Day 90 and Day 180. A blinded panel will compare photographs and provide a qualitative assessment of overall improvement in submental area between the photos using a five-point scale (1= “Much Improved”, 2= “Minimally Improved”, 3= “No Change from Baseline”, 4= “Minimally Worse”, 5= “Much Worse”). Tables will summarize the ratings by reader and the median of the three readers by subject in both the ITT and PP populations at each visit. The summary will include the number and percentage of subjects in each of the categories and the two-sided Clopper-Pearson 95% CI of the percentages. Additionally, a binomial test of proportions will test improvement, by testing those grouped as “Much Improved” or “Minimally Improved” verse all others.

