7.5. Blinding

This study is open-label however, photo images collected during the study will be evaluated qualitative by a panel of three qualified raters whom will be blinded (i.e., will not know) to the date and time when the photo images were collected. Each rater will evaluate the images independent of each other and will provide their respective photo image qualitative assessment for analysis.

Investigational Device: ThermiRF

Protocol No.: Thermi_0005

Version Date: Final 10-May-2016

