11.5.2 Secondary Effectiveness Analyses

Analysis of all effectiveness endpoints will be conducted on the ITT population and on the PP population. Continuous endpoints will be tested using the paired *t*-test, ordinal endpoints will use the Wilcoxon-Pratt signed rank test, and binary endpoints will be tested using the binomial proportion test.

Raters' assessment of improvement will be validated based on a comparison of the blinded raters' assessments to unblinded raters' assessments at Day 60 as outlined in Kim et al. (Kim et al. 2004) using 30 subjects at Day 60 selected at random. Two unblinded clinicians, who know which photos are baseline and which are Day 60, will assess the 2D photography at baseline and Day 60. Three blinded clinicians, who do not know which photos are baseline and which are Day 60, will assess the same photos. The assessments of the unblinded and blinded raters will be compared using Cohen's unweighted kappa statistic (Fleiss et al. 1969). The assessments will be considered validated according to the scale detailed by Landis et al. (Landis & Koch 1977), where <0.00 is considered poor agreement, 0.00-0.20 is slight agreement, 0.21-0.40 is fair agreement, 0.41-0.60 is moderate agreement, 0.61-0.80 is substantial agreement, and >0.80 is almost perfect agreement. Accordingly, any score greater than 0.60 will validate the method.

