**Protocol:** *An Open-Label, Single-Center, Single-Treatment, Safety and Effectiveness Evaluation of Percutaneous Radiofrequency in Achieving Submental Lift*  
**Version:** Protocol Rev. A; SAP Rev. B

Table 7.1.1 Study Endpoints – Qualitative Assessment for the 2D Imaging ITT Population [1]		
	Percent Agreement	Kappa Statistic [2]
Overall		
	XX.X (X/XX)	X.XXX
Subgroups [3]		
Reader 1-2	XX.X (X/XX)	X.XXX
Reader 1-3	XX.X (X/XX)	X.XXX
Reader 1-4	XX.X (X/XX)	X.XXX
Reader 1-5	XX.X (X/XX)	X.XXX
Reader 2-3	XX.X (X/XX)	X.XXX
Reader 2-4	XX.X (X/XX)	X.XXX
Reader 2-5	XX.X (X/XX)	X.XXX
Reader 3-4	XX.X (X/XX)	X.XXX
Reader 3-5	XX.X (X/XX)	X.XXX
Reader 4-5	XX.X (X/XX)	X.XXX

[1] 30 subjects in sequential order of enrollment chosen for 60 day visit.

[2] Readers compared using Cohen's unweighted Kappa statistic

[3] Readers 1 and 2 were unblinded to image visit date, Readers 3, 4, and 5 were blinded to image visit date.

Listing 7.1.1 Study Endpoints – Qualitative Assessment for the 2D Imaging						
Subject ID	Analysis Population	Reader 1	Reader 2	Reader 3	Reader 4	Reader 5
XX-XXX	XX	XX	XX	XX	XX	XX

**Sponsor:** ThermiGen, LLC.  
**Protocol Number:** Thermi\_0005  
**Protocol:** *An Open-Label, Single-Center, Single-Treatment, Safety and Effectiveness Evaluation of Percutaneous Radiofrequency in Achieving Submental Lift*  
**Version:** Protocol Rev. A; SAP Rev. B

Table 7.1.2 Study Endpoints – Qualitative Assessment for the 2D Imaging at Day 60 ITT Population [1]					
	Reader 1 [2]	Reader 2 [2]	Reader 3 [3]	Reader 4 [3]	Reader 5 [3]
Based on your perceived Baseline vs. Day 60, how would you rate observed submental area change at Day 60?					
Much Improved	XX.X (X/XX)				
Minimally Improved	XX.X (X/XX)				
No change from Baseline	XX.X (X/XX)				
Minimally Worse	XX.X (X/XX)				
Much Worse	XX.X (X/XX)				

[1] 30 subjects in sequential order of enrollment chosen for 60 day visit.

[2] Reader unblinded to image visit date.

[3] Reader blinded to image visit date.

Listing 7.1.2 Study Endpoints – Qualitative Assessment for the 2D Imaging						
Subject ID	Analysis Population	Reader 1	Reader 2	Reader 3	Reader 4	Reader 5
XX-XXX	XX	XX	XX	XX	XX	XX

**Sponsor:** ThermiGen, LLC.  
**Protocol Number:** Thermi\_0005  

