Subject ID	Analysis Population	Improvement? (All reasons)	Skin Feel?	Satisfaction?	Recommend?	Improvement? (All reasons)	Skin Feel?	Satisfaction?	Recommend?	Improvement? (All reasons)	Skin Feel?	Satisfaction?	Recommend?	
XX-XXX	XX	XX	XX	XX	XX	XX	XX	XX	XX	XX	XX	XX	XX	

**Sponsor:** ThermiGen, LLC.  
**Protocol Number:** Thermi\_0005  
**Protocol:** *An Open-Label, Single-Center, Single-Treatment, Safety and Effectiveness Evaluation of Percutaneous Radiofrequency in Achieving Submental Lift*  
**Version:** Protocol Rev. A; SAP Rev. B

Table 7.2.5 Study Endpoints – Qualitative Assessment for the 2D Imaging at Day 90 and Day 180 compared to Baseline ITT Population								
	Day 90							
	Reader 1	95% CI [1]	Reader 2	95% CI [1]	Reader 3	95% CI [1]	Total [3]	95% CI [1]
Much Improved	XX.X (X/XX)	(X.X, X.X)	XX.X (X/XX)	(X.X, X.X)	XX.X (X/XX)	(X.X, X.X)	XX.X (X/XX)	(X.X, X.X)
Minimally Improved	XX.X (X/XX)	(X.X, X.X)	XX.X (X/XX)	(X.X, X.X)	XX.X (X/XX)	(X.X, X.X)	XX.X (X/XX)	(X.X, X.X)
No change	XX.X (X/XX)	(X.X, X.X)	XX.X (X/XX)	(X.X, X.X)	XX.X (X/XX)	(X.X, X.X)	XX.X (X/XX)	(X.X, X.X)
Minimally Worse	XX.X (X/XX)	(X.X, X.X)	XX.X (X/XX)	(X.X, X.X)	XX.X (X/XX)	(X.X, X.X)	XX.X (X/XX)	(X.X, X.X)
Much Worse	XX.X (X/XX)	(X.X, X.X)	XX.X (X/XX)	(X.X, X.X)	XX.X (X/XX)	(X.X, X.X)	XX.X (X/XX)	(X.X, X.X)
Improvement								
Yes	XX.X (X/XX)	(X.X, X.X)	XX.X (X/XX)	(X.X, X.X)	XX.X (X/XX)	(X.X, X.X)	XX.X (X/XX)	(X.X, X.X)
No	XX.X (X/XX)	(X.X, X.X)	XX.X (X/XX)	(X.X, X.X)	XX.X (X/XX)	(X.X, X.X)	XX.X (X/XX)	(X.X, X.X)
p-value [2]	X.XXX		X.XXX		X.XXX		X.XXX	
Day 180								
Much Improved	XX.X (X/XX)	(X.X, X.X)	XX.X (X/XX)	(X.X, X.X)	XX.X (X/XX)	(X.X, X.X)	XX.X (X/XX)	(X.X, X.X)
Minimally Improved	XX.X (X/XX)	(X.X, X.X)	XX.X (X/XX)	(X.X, X.X)	XX.X (X/XX)	(X.X, X.X)	XX.X (X/XX)	(X.X, X.X)
No change	XX.X (X/XX)	(X.X, X.X)	XX.X (X/XX)	(X.X, X.X)	XX.X (X/XX)	(X.X, X.X)	XX.X (X/XX)	(X.X, X.X)
Minimally Worse	XX.X (X/XX)	(X.X, X.X)	XX.X (X/XX)	(X.X, X.X)	XX.X (X/XX)	(X.X, X.X)	XX.X (X/XX)	(X.X, X.X)
Much Worse	XX.X (X/XX)	(X.X, X.X)	XX.X (X/XX)	(X.X, X.X)	XX.X (X/XX)	(X.X, X.X)	XX.X (X/XX)	(X.X, X.X)
Improvement								
Yes	XX.X (X/XX)	(X.X, X.X)	XX.X (X/XX)	(X.X, X.X)	XX.X (X/XX)	(X.X, X.X)	XX.X (X/XX)	(X.X, X.X)
No	XX.X (X/XX)	(X.X, X.X)	XX.X (X/XX)	(X.X, X.X)	XX.X (X/XX)	(X.X, X.X)	XX.X (X/XX)	(X.X, X.X)
p-value [2]	X.XXX		X.XXX		X.XXX		X.XXX	

[1] Two-sided 95% Clopper-Pearson confidence interval.

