[2] p-value from Binomial Proportion Test for proportion of subjects who were marked "Much Improved" or "Minimally Improved"

[3] Median of 3 Reader's scores

Listing 7.2.5 Study Endpoints – Qualitative Assessment for the 2D Imaging								
Subject ID	Analysis Population	Day 90			Day 180			Reader 3
		Reader 1	Reader 2	Reader 3	Reader 1	Reader 2	Reader 3	
XX-XXX	XX	XX	XX	XX	XX	XX	XX	

**Sponsor:** ThermiGen, LLC.  
**Protocol Number:** Thermi\_0005  
**Protocol:** *An Open-Label, Single-Center, Single-Treatment, Safety and Effectiveness Evaluation of Percutaneous Radiofrequency in Achieving Submental Lift*  
**Version:** Protocol Rev. A; SAP Rev. B

[figure not shown]
Table 7.3						
Study Endpoints - Exploratory Endpoint Elasticity						
ITT Population with Available Data						
		Baseline N=	Day 90 N=		Day 180 N=	
Assessment		Mean ± SD (N) Median (Min, Max)	95% CI [1]	Mean ± SD (N) Median (Min, Max)	95% CI [1]	Mean ± SD (N) Median (Min, Max)
Elasticity						
R0	XX.X ± XX.X (XX) XX.X (XX, XX)	(X.X, X.X)	XX.X ± XX.X (XX) XX.X (XX, XX)	(X.X, X.X)	XX.X ± XX.X (XX) XX.X (XX, XX)	(X.X, X.X)
R2	XX.X ± XX.X (XX) XX.X (XX, XX)	(X.X, X.X)	XX.X ± XX.X (XX) XX.X (XX, XX)	(X.X, X.X)	XX.X ± XX.X (XX) XX.X (XX, XX)	(X.X, X.X)
R5	XX.X ± XX.X (XX) XX.X (XX, XX)	(X.X, X.X)	XX.X ± XX.X (XX) XX.X (XX, XX)	(X.X, X.X)	XX.X ± XX.X (XX) XX.X (XX, XX)	(X.X, X.X)
R7	XX.X ± XX.X (XX) XX.X (XX, XX)	(X.X, X.X)	XX.X ± XX.X (XX) XX.X (XX, XX)	(X.X, X.X)	XX.X ± XX.X (XX) XX.X (XX, XX)	(X.X, X.X)
R9	XX.X ± XX.X (XX) XX.X (XX, XX)	(X.X, X.X)	XX.X ± XX.X (XX) XX.X (XX, XX)	(X.X, X.X)	XX.X ± XX.X (XX) XX.X (XX, XX)	(X.X, X.X)
Change from Baseline Elasticity						
R0	N/A	N/A	XX.X ± XX.X (XX) XX.X (XX.X, XX.X)	(X.X, X.X)	XX.X ± XX.X (XX) XX.X (XX, XX)	(X.X, X.X)
R2	N/A	N/A	XX.X ± XX.X (XX) XX.X (XX.X, XX.X)	(X.X, X.X)	XX.X ± XX.X (XX) XX.X (XX, XX)	(X.X, X.X)
R5	N/A	N/A	XX.X ± XX.X (XX) XX.X (XX.X, XX.X)	(X.X, X.X)	XX.X ± XX.X (XX) XX.X (XX, XX)	(X.X, X.X)
R7	N/A	N/A	XX.X ± XX.X (XX) XX.X (XX.X, XX.X)	(X.X, X.X)	XX.X ± XX.X (XX) XX.X (XX, XX)	(X.X, X.X)
R9	N/A	N/A	XX.X ± XX.X (XX) XX.X (XX.X, XX.X)	(X.X, X.X)	XX.X ± XX.X (XX) XX.X (XX, XX)	(X.X, X.X)

[1] Two-sided 95% confidence interval of the percentage or the mean.

[figure not shown]
Listing 7.3				
Study Endpoints - Exploratory Endpoint Elasticity				

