[2] Readers compared using Cohen's unweighted Kappa statistic

[3] Readers 1 and 2 were unblinded to image visit date, Readers 3, 4, and 5 were blinded to image visit date.

Listing 9.1.1 Study Endpoints – Qualitative Assessment for the 2D Imaging						
Subject ID	Analysis Population	Reader 1	Reader 2	Reader 3	Reader 4	Reader 5
XX-XXX	XX	XX	XX	XX	XX	XX

**Sponsor:** ThermiGen, LLC.  
**Protocol Number:** Thermi\_0005  
**Protocol:** *An Open-Label, Single-Center, Single-Treatment, Safety and Effectiveness Evaluation of Percutaneous Radiofrequency in Achieving Submental Lift*  
**Version:** Protocol Rev. A; SAP Rev. B

Table 9.1.2 Study Endpoints – Qualitative Assessment for the 2D Imaging PP Population [1]					
	Reader 1 [2]	Reader 2 [2]	Reader 3 [3]	Reader 4 [3]	Reader 5 [3]
Based on your perceived Baseline vs. Day 60, how would you rate observed submental area change at Day 60?					
Much Improved	XX.X (X/XX)				
Minimally Improved	XX.X (X/XX)				
No change from Baseline	XX.X (X/XX)				
Minimally Worse	XX.X (X/XX)				
Much Worse	XX.X (X/XX)				

[1] 30 subjects in sequential order of enrollment chosen for 60 day visit.

[2] Reader unblinded to image visit date.

[3] Reader blinded to image visit date.

Listing 9.1.2 Study Endpoints – Qualitative Assessment for the 2D Imaging						
Subject ID	Analysis Population	Reader 1	Reader 2	Reader 3	Reader 4	Reader 5
XX-XXX	XX	XX	XX	XX	XX	XX

**Sponsor:** ThermiGen, LLC.  
**Protocol Number:** Thermi\_0005  
**Protocol:** *An Open-Label, Single-Center, Single-Treatment, Safety and Effectiveness Evaluation of Percutaneous Radiofrequency in Achieving Submental Lift*  
**Version:** Protocol Rev. A; SAP Rev. B

Table 9.2.1 Secondary Endpoint – P-GAIS PP Population with Available Data						
	Day 60 [1]		Day 90		Day 180	
Assessment		95% CI[2]		95% CI[2]		95% CI[2]
Physician - Global Aesthetic Improvement Scale (P-GAIS)						
5 (Very Much Improved)	XX.X (X/XX)	(X.X, X.X)	XX.X (X/XX)	(X.X, X.X)	XX.X (X/XX)	(X.X, X.X)
4 (Much Improved)	XX.X (X/XX)	(X.X, X.X)	XX.X (X/XX)	(X.X, X.X)	XX.X (X/XX)	(X.X, X.X)
3 (Improved)	XX.X (X/XX)	(X.X, X.X)	XX.X (X/XX)	(X.X, X.X)	XX.X (X/XX)	(X.X, X.X)
2 (No Change)	XX.X (X/XX)	(X.X, X.X)	XX.X (X/XX)	(X.X, X.X)	XX.X (X/XX)	(X.X, X.X)
1 (Worse)	XX.X (X/XX)	(X.X, X.X)	XX.X (X/XX)	(X.X, X.X)	XX.X (X/XX)	(X.X, X.X)
p-value [3]	X.XXX		X.XXX		X.XXX	

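### No stated step converts the blinded 2D photo ratings to the true photo order, so if readers do not know the order the improved rate can be biased up or down

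*SAP*

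**What the plan says.** Protocol 7.5 describes three raters who are "blinded (i.e., will not know) to the date and time when the photo images were collected". For the Day 60 validation, Protocol 11.5.2 adds three blinded clinicians "who do not know which photos are baseline and which are Day 60, will assess the same photos". Footnote 3 to SAP Tables 7.1.1 and 9.1.1 repeats this: "Readers 3, 4, and 5 were blinded to image visit date". The Day 60 shells (Tables 7.1.2 and 9.1.2) put this question to readers: "Based on your perceived Baseline vs. Day 60, how would you rate observed submental area change at Day 60".

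For Days 90 and 180, SAP 10.2.6 states: "A blinded panel will compare photographs and provide a qualitative assessment of overall improvement in submental area between the photos using a five-point scale". The scale is directional: 1 is much improved, 3 is no change from baseline, 5 is much worse. The plan reports each reader and the median of the three, and tests categories 1 and 2 against the rest. Table 7.2.5 is titled "Qualitative Assessment for the 2D Imaging at Day 90 and Day 180 compared to Baseline", and its footnote 2 defines the test as "p-value from Binomial Proportion Test for proportion of subjects who were marked" in either of the two improved categories.

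The Day 60 ratings are compared by unweighted kappa. Protocol 11.5.2 says "any score greater than 0.60 will validate the method".

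**The concern.** A reader who does not know which photo came first can use an improved-to-worse scale only by deciding which photo to treat as baseline. If that decision is wrong, the rating points the wrong way: a worsened pair is marked improved, and an improved pair is marked worse. The usual remedy is to record the reader's choice and reverse the score against the photo key. Neither document describes that step. Listings 7.1.1, 7.1.2, 7.2.5, 9.1.1, 9.1.2 and 9.2.5 carry reader scores but no column for true or perceived order. Protocol 11.6 assigns specific derivations to the SAP, so the rule belongs there.

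This matters because the panel reading is the only efficacy assessment described as blinded in an open-label, single-arm study. Without conversion, its improved rate mixes the treatment effect with readers' guesses about order.

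**Working it through.** The plan states no expected rate, sample size or power for this endpoint, so there is no figure to reproduce. The check is textual, followed by an illustration on assumed inputs.

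**1. What is explicit and what is inferred**

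- Day 60: readers do not know which photo is baseline, rate against a perceived baseline, and have their ratings tabulated as marked. All of this is explicit.
- Days 90 and 180: the panel is blinded to date and time, uses the same directional scale, and has its ratings counted as marked. That readers also do not know the order is an inference from the general blinding.
- At no visit is there a recorded perceived order, a check against the true order, or a recoding step.

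**2. Order guessed from appearance.** Let q be the share of pairs in which the follow-up photo truly looks better, w the share in which it looks worse, and g the probability that a reader takes the better-looking photo as the follow-up. Assume g does not depend on the true order.

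- Unconverted improved rate: g(q + w). True rate: q.
- The unconverted rate is too high if g > q/(q + w), and too low if g is smaller.
- Share of pairs given the wrong direction: q(1 − g) + wg.
- Median of three readers who see the same differences but guess order independently: replace g by g²(3 − 2g).

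The number of pairs is taken as 61 (70 × 0.875 = 61.25, using the plan's 12.5% dropout).

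| Assumed case | True rate | One reader | Median of three | Wrong direction |
|---|---|---|---|---|
| A: q = w = 0.40, g = 0.7 | 40% | 0.7 × 0.80 = 56% | 0.784 × 0.80 = 63% | 0.40, about 24 of 61 |
| B: q = 0.70, w = 0.10, g = 0.6 | 70% | 0.6 × 0.80 = 48% | 0.648 × 0.80 = 52% | 0.34, about 21 of 61 |
| C: q = 0.70, w = 0.10, g = 0.8 | 70% | 0.8 × 0.80 = 64% | 0.896 × 0.80 = 72% | 0.22, about 13 of 61 |

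With q + w = 0.80, moving g from 0.5 to 1 takes the one-reader rate from 40% to 80%, whether the true rate is 40% or 70%. The last column is per reader.

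**3. Order reversed at random, unrelated to appearance.** With reversal probability e, the unconverted rate is q(1 − e) + we. For q = 0.60 and w = 0.10 it is 55% at e = 0.10, 47.5% at e = 0.25 and 35% at e = 0.50, against a true 60%. For q = 0.20 and w = 0.40 it is 25% at e = 0.25, against a true 20%. Here too the error goes in both directions.

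**4. Would the Day 60 kappa catch it?** I simulated 30 pairs over 4,000 runs. The assumptions were that 30% of differences are rated 'much', order calls are independent at the same g, and the unblinded readers use the true order. With full agreement on the size of change, the mean of the six blinded-versus-unblinded kappas averages 0.475 (A), 0.538 (B) and 0.674 (C). It exceeds 0.60 in about 6%, 21% and 83% of runs. Adding 10% one-step size errors lowers these to under 1%, under 1% and about 6%.

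**The case against.** The strongest reply is that the gap is not shown at Days 90 and 180. The perceived-baseline wording is confined to the Day 60 shells, where it also heads the columns of the two unblinded readers. For the later visits, the scale's middle category and the Table 7.2.5 title both refer to baseline. That fits readers being shown a labelled baseline, or decoding before tabulation. The rater guideline (Protocol Appendix 10) is held in the Trial Master File, and the case report forms cited in SAP section 2 are not reproduced; either may already record order. The kappa is a real safeguard, since an inverted rating of a changed pair counts as disagreement and cases A and B would usually miss 0.60. Case C passes more often, but its median is only about two points off.

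Much of this stands. A reader might infer that the ratings will go unconverted, or that the Day 90 and 180 results will be wrong. The documents support neither; they support only that no conversion is stated. The references to baseline show what is intended but describe no step that achieves it. Showing readers a labelled baseline would need reconciling with Protocol 7.5. The kappa covers 30 subjects at Day 60 and recodes no rating at any visit. What follows if it fails is also unstated, but that is a separate question.

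**Conclusion.** The point holds as a conditional one. At Day 60, order-blind directional ratings are tabulated without a stated conversion. At Days 90 and 180 the same scale is counted as marked, and if readers do not know the order there either, the improved rate can be biased in either direction. The median of three does not remove this: it moves case A further from the truth (63% against 40%) and brings case B only slightly closer (52% against 70%).

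The size is unknown. Every q, w, g and e above is an assumption, and the figures show only that the error can be material and can go either way. The SAP states no null for the 2D binomial test, so I attach no error rate to it.

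This should be fixed, but its reach is limited. It concerns one of five secondary assessments, SAP 7.5 rules out formal testing of them for labeling claims, and the primary 3D endpoint is untouched.

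**What to change.** In SAP 10.2.1 and 10.2.6, state whether readers know which photo is baseline. If they do not:

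1. Record which photo each reader took as baseline.
2. Where that choice is wrong, mirror the rating (1↔5, 2↔4, 3 unchanged). Do this before the Day 60 kappa, the three-reader median and the improved/not-improved split.
3. Add the true and perceived order to Listings 7.1.1, 7.1.2, 7.2.5, 9.1.1, 9.1.2 and 9.2.5, and use converted scores in the dependent tables.

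If the reading form or the rater guideline already does this, one sentence in 10.2.6 citing the rule is enough.

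The cost is one form field, one derivation and some listing columns, with no extra images or readers. The reported improved rate may move either way. Rereading is needed only if perceived order was not captured: about 61 × 2 visits × 3 readers = 366, plus 30 × 3 = 90 at Day 60, or 456 pair readings. If all 70 subjects have photos at both visits, the total is 420 + 90 = 510.
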